Following Exposure to Study Drugs: Another concern is the possibility that exposure of participants with no histories of drug abuse to drugs in our research setting might in some way increase the likelihood of these individuals to begin abusing illicit drugs when they return to the community. The Johns Hopkins IRB closely monitors this issue, and has repeatedly concluded that administering drugs that have reinforcing effects to individuals who do not abuse drugs is not associated with an increased propensity to begin abusing drugs. Administering drugs that may have reinforcing effects to non-dependent users has substantial precedent in laboratory examinations of drug effects, and we have a rich and extensive history of utilizing this practice. Several research studies that have directly examined the association between

study-related drug administration and subsequent drug use behavior have failed to demonstrate that controlled, laboratory drug exposure increases the risk for developing future dependence. For example, authors of a recent study that administered methamphetamine to a sample of non treatment-seeking drug abusers reported no difference between-group differences in drug use behaviors, assessed via the Addiction Severity Index, at a 6-month follow-up assessment¹²⁶. Second, a systematic follow-up study reported that alcohol-dependent volunteers randomly assigned to laboratory studies either involving or not involving experimental alcohol consumption have not differed in their follow-up outcomes¹²⁷. Third, a recent study concluded that investigational administration of intravenous cocaine to intravenous inexperienced cocaine users did not increase the risk of recreational intravenous use¹²⁸. Fourth, a study conducted by our research team administered cocaine and/or opioids to participants with histories of drug abuse and observed no significant changes in number of days of reported drug use, dollar amounts reported spent for various drug classes, or any increases in Addiction Severity Index domain scores at a one month follow-up¹²⁹. Finally, the College on the Problems of Drug Dependence, a prestigious international association of drug dependence researchers, supports the practice of enrolling non treatment-seeking individuals into drug abuse liability evaluation studies. Specifically, the College on Problems of Drug Dependence reported that exposure of drug abusers to abused drugs in a controlled research setting does not enhance the desire of an individual to use drugs, worsen addiction, or make addiction more difficult to treat¹³⁰. Overall, given the substantial data available in the literature and our own laboratory experience, we feel confident that administration of small quantities of psychoactive drugs to individuals with recreational histories of drug abuse will not be associated with future drug use behavior.

Participants will also not be informed about the specific medication they are receiving, which is a common procedure used by our research unit to minimize bias in responding. This procedure also makes it difficult for the participant to seek out drugs they may have found reinforcing during the study session, thus further minimizing the opportunity for study participation to increase risk of non-study drug abuse.

d. Protection Against Risks of Discomfort from Pain Testing: It is likely that participants will experience some acute and transient discomfort from the pain testing session, however we will work to mitigate that risk as much as possible. First, participants will be informed of the pain testing procedure during the informed consent and will be able to make an informed decision regarding their study participation. Second, we chose standardized pain tests that are known to produce short-lived effects and thus are unlikely to produce any residual pain. Third, the measures rely on the participant ending the pain testing procedure as an outcome measure, which means that all participants are encouraged to remove themselves from the painful stimulus at any time and that they are in control of the magnitude and duration of pain they experience. Fourth, we will enforce an upper limit on all pain measures to prevent any tissue damage from occurring (e.g., hand cannot be in cold pressor task for >300 seconds). Fifth, participants will be informed that they can revoke their consent to participate in the pain testing at any time without penalty. Specific to capsaicin- one of the primary risks of capsaicin is that it could be accidentally transferred to another part of the body. To prevent this from happening, we will make sure the exposure site is well-marked and that all residual topical cream is removed with alcohol pads once the cream has been mostly absorbed. We will also be able to apply ice to the exposure site to reduce any persistent discomfort associated with capsaicin. Finally, the participants will be monitored by study staff and will have access to medical care and concomitant medications to treat residual pain if necessary. We will also document and submit to our IRB all adverse events reported from the pain testing session and will follow any recommendations they may have regarding the cessation of pain testing. Across hundreds of research participants with various conditions, we have had no adverse events deemed greater than mild (even this level AE occurs in < 1/100 cases) related to the use of these devices.

e. IV Placement and Blood Draws: These procedures are routinely performed without incident in medical settings and will be performed by a certified phlebotomist. Additionally, these procedures will only occur in a subset of participants that volunteer to undergo these procedures and can be stopped at any time without penalty.

f. Knee X-Rays: The X-rays will be read by a radiologist from the Division of Radiology within the Russell Morgan Department of Radiology, JHU. If they occur, incidental findings will be communicated to the study investigators who will communicate the result to the subject and an appropriate referral will be made if clinically indicated.

g. Physical Functioning Tasks: Minimal risks are associated with the 3 minute walk test, stair climb and timed up and go task, as these activities are part of everyday activity for most people. Should participants feel pain and be unable or unwilling to continue, they are instructed that they may stop at any time.

h. Protection Against Risks Associated with Breach of Confidentiality: To protect confidentiality, all research participants will be assigned unique participant identification codes that will be used on all study-related forms and online websites. Documents that include the participants' full names (e.g., signed informed consent forms) will be stored in an independent binder, consistent with FDA Good Clinical Practice Guidelines, and will be kept in a locked room. Confidential information will never be shared with anyone outside of the research program without the explicit written permission of the research participant. Only selected designated staff members will be approved to share confidential information after explicit written permission is obtained from the participant and the participant will be able to revoke written permission at any time. In accordance with IRB requirements, all research staff will be formally trained in these procedures. No identifying participant information will be used in written reports, manuscripts and/or conference presentations

c. Plan for reporting unanticipated problems or study deviations.

All adverse events will be reported to the IRB and other relevant agencies (e.g., FDA, NIDA) as required. The Principal Investigator and Co-investigators are responsible for reporting such events.

d. Legal risks such as the risks that would be associated with breach of confidentiality.

Although there is always a small risk that confidentiality will be breached, we believe this risk to be very minimal with the current study. It is possible that participants' urine samples may test positive for the study drugs for up to 1 week after each session. To mitigate any potential negative impact this may have on participants, we will inform them of this potential risk in the ICF so they may make an informed decision regarding their participation despite this potential consequence, and will provide any interested participants (who sign a release of information) with a letter signed from the study investigator stating that their urine sample may be positive for drugs that can be considered abusable for up to 7 days following a study session.

e. Financial risks to the participants.

None.

9. Benefits

a. Description of the probable benefits for the participant and for society.

There is no direct benefit of this study to the participant. However, this study will provide the first empirical evidence in humans of the magnitude and duration by which cannabinoids may enhance opioid analgesic effects in OA patients, using a standardized quantitative sensory testing (comprehensive pain testing) battery. This information will advance the use of cannabinoids from treatment-refractory conditions to more wide-spread use for pain treatment. A positive result will provide new medication targets and will help lead efforts to reduce societal reliance upon opioids for the treatment of pain. Reduced availability of opioids will lead to reductions in use/abuse and related problems (risky injection behavior, opioid overdose).

10. Payment and Remuneration

a. Detail compensation for participants including possible total compensation, proposed bonus, and any proposed reductions or penalties for not completing the protocol.

This study is moderately intense so, given the older age (45+) of the population and the multiple drug and pain testing exposures, we have set compensation accordingly. Based on our extensive experience, remuneration will need to compensate for lost workdays and other inconveniences and will need to be high enough to encourage continued retention so that we are able to complete the study in the proposed period of time. Subjects will earn \$100 for the in-person screening visit, and \$150 for completing the first, \$200 for the second, \$250 for the third, and \$325 for the fourth experimental session. For subjects that choose to participate in the blood drawing aspect of the study, an additional \$100 will be earned for each session. Participants will be offered \$25 for each hair sample provided, for a total of \$50 for the optional substudy. We frequently use this approach to compensate subjects for individual sessions AND study completion, and found it to successfully promote retention in studies over multiple weeks.

11. Costs

a. Detail costs of study procedure(s) or drug (s) or substance(s) to participants and identify who will pay for them.

All study related procedures will be paid by a National Institute on Drug Abuse grant; participants will not incur any direct cost for study participation.

Reference List

- (1) Portenoy RK. Current pharmacotherapy of chronic pain. *J Pain Symptom Manage* 2000;19:S16-S20.
- (5) Center for Disease Control. Drug Poisoning Deaths in the United States, 1980-2008. *NCHS Data Brief* [serial online] 2011;No. 81.
- (6) Centers for Disease Control and Prevention. Prescription Drug Overdose in the United States: Fact Sheet. *CDC* [serial online] 2014.
- (8) Tauben D. Nonopiod medications for pain. *Phys Med Rehabil Clin N Am* 2015;26:219-248.

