dronabinol reaches peak concentrations in 2-4 hours and is 90-95% absorbed but, due to extensive first-pass metabolism, is only 10-20% bioavailable. It is excreted in fecal (35-50%) and renal (10-15%) waste. The elimination half-life is biphasic, with an initial half-life of 4 hours and a terminal half-life of 25-36 hours, and an active metabolite (11-hydroxy-delta-9-THC) is produced. There is no current evidence that dronabinol is differentially affected by P450 status. Dronabinol is sold commercially in 2.5mg, 5mg, and 10mg dose ranges. **We have chosen to administer a 0 mg (placebo) and 10mg dose of dronabinol in this study**, which is within the range currently prescribed for chemotherapy-induced nausea and vomiting and AIDS-related anorexia, and therefore will have direct clinical applicability. Dronabinol will be purchased as a capsule and will be over-encapsulated by our research pharmacy to ensure double-blind administration procedures. Placebo doses will consist of lactose or another benign weight-matched filler.

Pharmacokinetic (pK) Analyses: Blood samples, drawn on a subset of participants, will enable direct comparison of serum drug levels with outcomes for the study aims (e.g., analgesia and physical functioning, subjective and observer- rated effects, abuse liability measures, and cognitive performance). We have chosen to sample pK at numerous timepoints to examine whether the duration of effects changes as a function of drug administration and determine whether behavioral changes following hydromorphone/dronabinol co-administration result from pharmacological enhancement or whether co-administration modifies the metabolic profile of either drug in such a way that it changes their duration of action. pK analysis is considered critical for this initial stage of evaluating drug-drug interactions¹³⁵ and will directly inform decisions regarding specific opioid/cannabinoid dose combinations that may be most appropriate to advance into clinical trials for the treatment of pain.

- b. Justification and safety information if FDA approved drugs will be administered for non-FDA approved indications or if doses or routes of administration or participant populations are changed.

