Hydromorphone: Hydromorphone hydrochloride is a pure mu opioid agonist that can be administered in oral, rectal, intramuscular (IM) or intravenous (IV) formulations for the indication of acute and/or chronic pain. We have chosen to administer hydromorphone because we have extensive experience administering hydromorphone in all formulations^{96; 109-117}, and know that it will produce reliable and consistent results that will aid interpretation of outcomes. Hydromorphone was also selected as the exemplar opioid for this study because it is not subject to differences in CYP metabolic enzymes and therefore will not require us to screen out individuals with recent exposure to CYP inhibiting or inducing medications, or to analyze and statistically control for CYP metabolic profiles in individual subjects. There is also no apparent effect of gender on the pharmacokinetics of hydromorphone. We have selected a low and mid-level dose because they are within the range of doses approved by the FDA. They are also sensitive to the QST tests we have proposed, and we therefore believe both will provide an ideal opportunity to evaluate whether the curve of hydromorphone is shifted as a function of dronabinol administration.

Dronabinol: Dronabinol is a schedule II drug that is being administered at 10 mg, which is consistent with the range approved by the FDA for therapeutic use in patients with chemotherapy-induced nausea and vomiting, and loss of appetite in patients with advanced HIV (AIDS). Dronabinol is also used off label for the treatment of Gilles de la Tourett's syndrome, general loss of appetite (related to cancer), spasticity from Multiple Sclerosis, treatment refractory and postoperative nausea and vomiting, and treatment refractory pruritus. When administered orally (as proposed here), dronabinol reaches peak concentrations in 2-4 hours and is 10-20% bioavailable. It is subject to extensive first-pass metabolism and is excreted in fecal (35-50%) and renal (10-15%) waste, with an elimination half-life of 19-36 hours.

We have selected oral dronabinol because it is FDA approved for pain conditions and more likely than nabilone to be prescribed in practice due to cost. We believe this approach will yield data that can be instantly utilized by pain treatment specialists, which increases the generalizability of our study approach.

c. Justification and safety information if non-FDA approved drugs without an IND will be administered.

N/A

7. Study Statistics

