b. Protection Against Dronabinol Risks: The majority of risks that are known to occur following dronabinol administration are psychiatric in nature. These risks are recognized as being transient and readily reversible. To mitigate these risks, we will exclude participants who endorse having previously experienced negative effects to cannabinoid products. We will also conduct psychiatric screening during the Screening session to ensure that patients with current or history of psychiatric events are excluded from study participation. Further, all participants will be informed about the potential side effects of the study medications and will be permitted to end study participation at any time if they experience negative events, with no consequences. Finally, we are providing participants with taxi service to and from the study sessions to ensure no persistent drug effects will impact their driving. We are also budgeting for the potential for a participant to stay the night at the CRU following study drug exposure. Based on our previous experience, we expect this to be a rare occurrence but are prepared to make that option available as needed.

To protect against risks of increased heart rate and tachycardia following co-administration of opioids and cannabinoids we will require all participants to be in good cardiovascular health prior to study enrollment (evidenced by a clean ECG, reviewed by a study physician). During sessions, all participants will be attached to a vital signs monitor and will have vital signs collected at 15 minute intervals for the first 2 hours to ensure safety. The risk of an opioid/cannabinoid interaction will only occur during a single study session, however since staff and participants will be blind as to the timing of that session, we will employ this monitoring schedule for all sessions. We will review data following completion of 5 participants and if it becomes evident that tachycardia is occurring regularly during any sessions, we will reevaluate the dose of study drugs being administered. However we believe that any changes to our dosing strategy are highly unlikely and this monitoring schedule will ensure participant safety during study participation.

c. Protection Against Risks That Participants May Begin Abusing Opioids or Cannabinoids

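### The 15-minute vital signs meant to guard against tachycardia on the combination end about when the protocol's own dronabinol peak window opens; running them to 4 hours after dosing is a cheap safety improvement

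*Combined protocol and SAP*

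**What the plan says.** Section 8.b, item b, states the purpose of its cardiovascular safeguards: "To protect against risks of increased heart rate and tachycardia following co-administration of opioids and cannabinoids". It requires good cardiovascular health with a clean ECG at entry. It then says "During sessions, all participants will be attached to a vital signs monitor" and that they "will have vital signs collected at 15 minute intervals for the first 2 hours to ensure safety". Because staff and participants do not know which session is the combination session, the same schedule applies to all sessions. The paragraph adds an early look at the data: "We will review data following completion of 5 participants and if it becomes evident that tachycardia is occurring regularly during any sessions", the doses will be reconsidered. It closes with the assurance that "this monitoring schedule will ensure participant safety during study participation".

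The timing of dronabinol is given twice. Section 6.a, item ii: "dronabinol reaches peak concentrations in 2-4 hours and is 90-95% absorbed". Section 6.b: "dronabinol reaches peak concentrations in 2-4 hours and is 10-20% bioavailable". Section 4.a (Experimental Sessions) puts administration of both capsules at about 1100.

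Other vital signs are planned. Section 4.a has them at regular but unspecified intervals after dosing. Section 7.d has them at every data collection point, with blood pressure and heart rate limits that prompt a call to a study physician. Section 7.d also names cardiovascular risk as the largest in the study.

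**The concern.** A safeguard written for one risk should be densest when that risk is expected to be highest. Tachycardia in the combination session is the named risk, and Section 8.a, item c, links it to THC or dronabinol in both studies it cites. The only timing that the protocol gives for dronabinol is a concentration peak at 2-4 hours, yet the densest readings cover the time up to 2 hours. Two hours fits the onset of hydromorphone (detectable at 15 minutes, Section 8.a) better than the dronabinol peak.

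At stake are how promptly a raised heart rate is seen in participants aged 45 or older, and what the five-participant dose review has to work with. Each participant has one combination session, so that review rests on five of them. If heart rate rises mainly after 2 hours, the review would judge it from the sparser part of the record.

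**Working it through.** There is no figure in the plan to reproduce. The check is clock arithmetic on the protocol's own times, followed by two calculations that rest on stated assumptions.

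**1. Overlap of schedule and peak window (documents only).**
- Dose: about 1100 (Section 4.a).
- End of 15-minute readings, counted from the dose: 1100 + 2 h = 1300.
- Dronabinol peak window: 1100 + 2 h to 1100 + 4 h = 1300 to 1500.
- Overlap: none beyond the reading at 1300 itself.

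**2. Readings in the window.**
- At 15-minute spacing, 0-2 h holds 120 / 15 = 8 readings, all of which are planned. The interval after 2 h and up to 4 h would also hold 120 / 15 = 8, none of which is planned under this rule.
- The spacing of the other vital signs after 2 h is an assumption. The pain battery repeats about every 90 minutes (Section 4.a, Pain Testing), which serves as the sparse end.

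| Assumed spacing after 2 h | Readings in 2-4 h, per session | Over 5 combination sessions |
|---|---|---|
| 90 min | 1-2 | 5-10 |
| 60 min | 2 | 10 |
| 30 min | 4 | 20 |
| 15 min (with the fix) | 8 | 40 |

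Readings within a session are correlated, so 40 readings are still five sessions. The gain is finer coverage in time, not eightfold or fourfold information.

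**3. How much of the exposure lies after 2 h (assumed curve).** Take a one-compartment curve, concentration proportional to exp(-ke·t) - exp(-ka·t). Section 6.a describes elimination "with an initial half-life of 4 hours", so ke = ln 2 / 4 = 0.173 per hour. Solving ln(ka/ke) / (ka - ke) = time of peak gives ka = 1.10, 0.57 and 0.35 per hour for peaks at 2, 3 and 4 h.
- Concentration at 2 h is 100, 94 and 83% of peak. With an assumed 1-hour absorption lag it is 100, 85 and 67%.
- Without a lag, 2-4 h carries 39-40% of the exposure over 0-6 h, and 0-2 h carries 21-31%.

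On this curve the dense schedule sees much of the rise in concentration, but the two hours after it carry more of the exposure.

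**4. Overlap with testing.** The assessment battery takes about an hour (Section 4.a, Measures). If all of it repeated every 90 minutes, 30 of every 90 minutes would be free: 120 × 30 / 90 = 40 minutes within 2-4 h, or 40 / 15 = 2.7 of the 8 readings on average (2 to 4, depending on alignment). The rest would be taken during pain or performance testing.

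**The case against.** The strongest reply is that participants are not left unobserved. They stay attached to a monitor, vital signs continue at data collection points, set limits prompt a call to a physician, an emergency department is across the street, and overnight stays are available. A reader might infer from the two-hour limit that monitoring ends at 2 hours; the documents contradict that. Only the 15-minute spacing ends. What they do not state, in the text that could be read, is the later interval, or whether the attached monitor alarms or records continuously. Table 2 may settle the interval, and if it is short most of the difference in step 2 disappears.

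A reader might also infer, because the start of the two hours is not stated, that they run from the session start at about 0800 and so end before any drug is given. That is not a sensible reading of a paragraph about risk after the two drugs are given together. The missing start point needs only a clarifying word.

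Third, a concentration peak is not a heart-rate peak. The protocol never times the cardiac effect, and an earlier one cannot be excluded. This stands, and it limits the point to a mismatch with the only timing that the protocol provides.

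Fourth, the risk is modest. Section 8.a, item c, reports tachycardia at 40 mg dronabinol that went away at 30 mg; this trial gives 10 mg. This also stands, although the other study cited there, of THC with oxymorphone, also reported tachycardia, and its dose is not given.

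Finally, the dose review looks at all sessions. Since heart rate is said to rise generally after THC, the five dronabinol-alone sessions inform it too. That is fair, but those sessions have the same schedule and the same drop in density at 2 hours.

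**Conclusion.** The point holds as a cheap improvement to patient safety. On the reading most favourable to the plan, the intensive schedule ends at about 1300 and the stated dronabinol peak window runs from about 1300 to 1500. This rests only on the dosing time, the two-hour limit and the 2-4 hour peak, all in the protocol. The assurance that the schedule will ensure safety therefore goes further than the schedule does.

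The size of the gap after 2 hours is not known. Eight readings per session with the change, against 1 to 4 without it, depends on assumed spacings of 90 to 30 minutes. The exposure shares depend on an assumed curve.

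A reader might go further and infer that the pharmacodynamic analysis of heart rate (Aim 4, Hyp8) is compromised. The documents do not support that: they give neither a time course nor a size for the heart-rate effect, and vital signs continue after 2 hours. No analysis error or loss of power is claimed.

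**What to change.** In Section 8.b, item b, state that vital signs are collected every 15 minutes from dosing to at least 4 hours after dosing, in all four sessions so that the blind is kept. This also settles the start point. Have the five-participant dose review look at heart rate in 0-2 h and 2-4 h separately, and note which readings were taken during or just after exercise or pain testing, so that a rise from testing is not mistaken for a drug effect. If Table 2 already gives 15-minute vital signs to 4 hours, a cross-reference is enough.

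The cost is up to 8 scheduled readings per session in 2-4 h, or 8 × 4 = 32 per participant, from a monitor already attached. Net of readings at the assumed later spacings it is about 4 to 7 per session, or 16 to 28 per participant. No visits are added. The downside is that some readings will fall within the test battery and the physical tests at projected peak, which adds some work for staff and makes those readings harder to interpret.
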